7. HYPOTHESIS, STATISTICS ANALYSIS AND SAMPLE SIZE

7.1.Hypothesis for the primary aim

Null hypothesis: There is no difference in KOOS subscore quality of life following ACI or AD treatment of a symptomatic cartilage defect ($>2 \text{ cm}^2$) in the weight bearing area of the knee 2 years after surgery.

The alternative hypothesis claims that differences between ACI and AD in KOOS quality of life subscore exist.

7.2.Statistical analysis

Demographic and clinical characteristics will be presented as means and standard deviations (SD) or frequencies and percentages, as appropriate. The normality of continuous data will be assessed by examining the histograms. If necessary, a suitable transformation will be considered to symmetrize the data.

Due to along follow-up period with 5 (7) measurement points, repeated observations will be available for each patient. A mixed model correctly adjusting for intra-patient correlations will be used to assess the trend in primary and secondary end-points. The model will contain random effects for intercepts and slopes, if significant. Fixed effects for time (likely non-linear) and group will be included together with the interaction between the two. The interaction will quantify possible differences between arms regarding time profiles and serve as an omnibus test. For continuous end-points, linear mixed model will be estimated, while generalized linear model will be fitted to dichotomous end-points. Relevant pairwise comparisons will be performed by deriving individual time point contrasts within each study arm. The results will be presented as estimated means of odds ratios together with the corresponding 95% confidence intervals (CI) and p-values. The estimates will further be adjusted for possible confounders such as age of the patient and severity of the cartilage lesion in the multivariate regression models.

The results with p-values below 0.05 will be considered statistically significant. Two-sided tests will be used. The data analysis will be conducted using SPSS v.22 (SPSS Inc, Chicago, Illinois) and SAS v 9.4.

7.3.Sample size

It has previously been shown that a change in subscore of 8-10 of KOOS QoL (quality of life) is clinically significant [48,49]. Therefore, for power analysis a difference in change of 10

between two treatment groups was assumed. A SD for change of 15 [32] was used. With the power of 80% and significance level of 5% the estimated minimum number of patients was 37 in each group. By adding 10% due to loss during follow-up, we therefore plan to include a total of 82 patients.

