13.2. Financing plan

14. TIME SCHEDULE AND PUBLICATION PLAN

14.1. Time schedule

14.2 Publication plan

15. STUDY ORGANIZATION

16. REFERENCES

1. STUDY SYNOPSIS: NCP – Autologous Chondrocyte Implantation

Topic	Details
Protocol Title:	Focal cartilage defects in the knee – A randomized controlled trial comparing Autologous Chondrocyte Implantation with arthroscopic debridement
Study Type:	Clinical
Indication:	Compare the effect of Autologous Chondrocyte Implantation (ACI) with arthroscopic debridement (AD) in patients with symptomatic full thickness knee cartilage injuries larger than 2cm ² .
Hypothesis Statement	
Focal cartilage injuries in the knee might have devastating effect both in the short term and in the long term. Various surgical treatment options are available; with ACI established as a recognized treatment method for larger lesions. Meta-analysis and systematic reviews have required well-designed, long-term, multicenter studies to evaluate clinical outcomes of ACI with the use of a “no treatment” group as a control group.
 
H0: There is no difference in KOOS QoL after ACI or AD from baseline to 24 months after surgery.
 
H1: There is a difference in KOOS QoL after ACI or AD from baseline to 24 months after surgery.

Study Objectives:	
Questionnaires: KOOS, Tegner score, Lysholm score, EQ-5D, VAS.
 
Physical examination: range of motion and hop test.
 
Radiology: x-ray and MRI of the knee.
 
Primary aim: KOOS quality of life (QoL) subscore.

Study Design:	Prospective, single-blinded parallel-group bicenter study with 2 treatment arms.
Duration of Study Participation:	Approx. 36 months inclusion and 24 months follow up. In total 5 years.
Follow-up Period:	24 months. All will be invited to participate in late controls after 5 and 10 years.
Study Location:	2 Norwegian hospitals: Akershus University Hospital and Oslo University Hospital – Ullevål.
Number of Planned Subjects:	82 patients
Study Population:	Inclusion: age 18-50 years old, single symptomatic cartilage defect on femoral condyle or trochlea, defect size larger than 2

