6.2. Primary endpoint

The Knee Injury and Osteoarthritis Outcome Score (KOOS) is a patient reported outcome measure validated to use in cartilage research studies and will enable comparison of our results with other reports. It assesses five domains; pain, symptoms, activity of daily living,

sport and recreational function and knee-related quality of life [44]. KOOS knee-related quality of life (QoL) subscore is the primary endpoint, where the primary aim is the difference in KOOS QoL subscore in the ACI group compared to the AD group at 2 years follow up. There will not be any interim analysis before 2 years follow up.

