14.2 Publication plan

The results will be published in peer reviewed orthopaedic journals, as well as presented to the orthopaedic community at national and international scientific meetings. They will also be actively communicated to the community by using the hospital web page with publication of the studies.

Upon study completion and finalization of the study report the results of this study will be submitted for publication and/or posted in a publicly assessable database of clinical study results.

[figure not shown]
The results of this study will also be submitted to the Competent Authority and the Ethics Committee according to EU and national regulations.

All personnel who have contributed significantly with the planning and performance of the study (Vancouver convention 1988) may be included in the list of authors.

The study will result in at least the following publications:

1. Autologous Chondrocyte Implantation versus Arthroscopic Debridement for the treatment of focal cartilage lesions of the weight bearing area of the knee. A randomized controlled trial – results at 24 months.
2. Cost related to Autologous Chondrocyte Implantation and Arthroscopic Debridement of cartilage lesions in the knee; considering the costs of surgery, hospitalization and follow-up, sick-leave and the need for secondary surgery.
3. Autologous Chondrocyte Implantation versus Arthroscopic debridement for the treatment of focal cartilage lesions of the weight bearing area of the knee. A randomized controlled trial – results at 5 years.

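### Random intercepts and slopes kept only if significant do not secure a correct standard error for the primary comparison; fix an unstructured covariance over the five visits in advance

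*Protocol*

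**What the plan says.** Section 7.2 plans a mixed model for the primary and secondary endpoints and says that it will account correctly for correlation within patients. On the covariance it says only: "The model will contain random effects for intercepts and slopes, if significant". It gives no criterion for significance and no time scale for the slope. The mean part is more flexible: "Fixed effects for time (likely non-linear) and group will be included together with the interaction between the two". The visits are unequally spaced (baseline, 3, 6, 12 and 24 months, section 6.3), and the model is introduced with "Due to along follow-up period with 5 (7) measurement points, repeated observations will be available for each patient".

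The synopsis (Overview of Statistical Plan) derives the primary comparison as a contrast from this model and likens it to a two-sample t-test.

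The protocol words the primary contrast in two ways. The synopsis hypothesis is about change: "There is no difference in KOOS QoL after ACI or AD from baseline to 24 months after surgery". The sample size follows that reading: "A SD for change of 15 [32] was used" (section 7.3). Section 6.2 instead states that "the primary aim is the difference in KOOS QoL subscore in the ACI group compared to the AD group at 2 years follow up".

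**The concern.** With categorical visit-by-arm means and complete data, the estimated difference is the same whatever covariance is used. The SE, confidence interval and p-value are not. A random intercept with one slope forces the variances and correlations over five visits into a form with at most four parameters. If patients differ in another way, for example because response appears early and then stays, that form can be wrong for exactly the contrast being tested. Choosing terms by significance does not protect against this: a retained slope can still be the wrong shape, and a dropped slope leaves equal correlation between all visits.

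At stake is the error rate of the primary test on the change reading, or its power on the 24-month reading. The contrasts announced in "Relevant pairwise comparisons will be performed by deriving individual time point contrasts within each study arm" are affected too: a within-arm change from baseline has the same ratio of model SE to true SE as the arm difference in change.

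**Working it through.** **The plan's own figure.** Difference 10, SD of change 15, 80% power, two-sided 5%. The normal approximation gives 2 × (1.960 + 0.842)² × 15² / 10² = 35.3, so 36 per arm. The noncentral t gives 37 (power 80.8%). Then 37 × 1.10 = 40.7, so 41 per arm and 82 in total. The plan's figure is reproduced, and nothing below changes it.

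**Target SE.** 15 × √(2/37) = 3.49. The 95% half-width is 1.9935 × 3.49 = 6.95 KOOS points.

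**Assumed true covariances.** Σ = (intercept variance) × J + (response variance) × zz′ + (residual variance) × I, where J is all ones and z is the response profile over 0, 3, 6, 12 and 24 months: step 0/1/1/1/1, plateau 0/.5/.8/1/1, or linear in months. The variance of 0-24 change is response + 2 × residual: 105 + 120, 145 + 80 and 65 + 160 all give 225, so the SD is 15 as in section 7.3. Two more patterns have the same SD of change: autoregressive (0.8 per visit) and compound symmetry (150, 0, 112.5). The split into components is an assumption; the protocol does not give it.

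**Method.** Fit the random-effects covariance V to Σ by likelihood. For contrast c, the SE ratio is r = √(c′Vc / c′Σc), and the large-sample type I error is 2 × [1 − Φ(1.96 r)].

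**Example by hand (step 120, 145, 40; intercept only).** Mean variance is (160 + 4 × 305)/5 = 276. Mean covariance is (4 × 120 + 6 × 265)/10 = 207. The implied variance of change is 2 × (276 − 207) = 138, so r = √(138/225) = 0.783 and type I error is 12.5%. With a slope linear in months, r = 0.827 and type I error is 10.5%.

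| Assumed pattern | Change, slope dropped | Change, months slope | Change, log slope | Change, piecewise (knot 3 months) | 24-month difference, SE ratio, months slope |
|---|---|---|---|---|---|
| Step 120/105/60 | 9.6% | 8.7% | 5.2% | 5.0% | 1.077 |
| Step 120/145/40 | 12.5% | 10.5% | 5.2% | 5.0% | 1.099 |
| Step 150/65/80 | 7.5% | 7.2% | 5.1% | 5.0% | 1.045 |
| Plateau 120/105/60 | 10.1% | 6.6% | 4.2% | 4.2% | 1.075 |
| Plateau 120/145/40 | 13.4% | 7.4% | 3.9% | 3.9% | 1.095 |
| Linear 120/105/60 | 10.6% | 5.0% | 5.7% | 5.0% | 1.000 |
| Autoregressive 0.8 | 13.4% | 4.6% | 3.8% | 3.7% | 1.078 |
| Compound symmetry | 5.0% | 5.0% | 5.0% | 5.0% | 1.000 |

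Under step or plateau with a months slope, the half-width for change is 6.95 × 0.827 = 5.75 to 6.95 × 0.938 = 6.5, instead of 6.95.

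**24-month difference.** Under step or plateau with a months slope, the SE is 4.5-9.9% too wide (up to 13% when visit number, square-root and log time are also tried). The assumed 24-month SDs are √285 = 16.9 to √305 = 17.5. With 37 per arm and a difference of 10, power is then 62.1-67.6% instead of 69.2-72.2%, a loss of 3.1-7.1 points. This direction needs the slope to be kept. If it is dropped, the step 120/145/40 pattern gives r = √(276/305) = 0.951 and 6.2%.

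**The rule itself, simulated.** 3,000 null trials per pattern, 41 per arm, 10% loss completely at random, slope kept by a 5% likelihood-ratio test, Monte Carlo error 0.4 points. Under step or plateau the type I error for change is 6.4-9.4% with a months slope and 4.3-5.5% with log time. Unstructured covariance gives 4.6-5.6% for change and 4.4-5.7% at 24 months over all eight patterns.

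**A second set of covariances.** With baseline correlated 0.35 with later visits, 0.7 between later visits and equal SDs, a months slope was kept in only 29% of runs and the type I error for change was 9.4%. With decaying correlation the slope was always kept and the rate was 4.3-4.4%. Unstructured gave 4.6-5.7% throughout (simulation error about 0.8 points).

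**The case against.** The strongest reply is that the harmful ingredient, a slope linear in months, is nowhere stated. Time scale, residual structure and degrees of freedom are usual content of an analysis plan that is not shown here. This stands in part: their absence is no fault of the protocol. What remains is the rule that the protocol does state, which ties the covariance to significance and does not deliver the correct adjustment that the same section promises.

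A reader might infer that no choice of time scale could rescue the rule. The text does not support that. It speaks of slopes in the plural and of non-linear time, so random piecewise slopes are compatible with it. A knot at 3 months gives 3.7-5.0% for change and 4.0-5.0% at 24 months over all eight patterns. Other compatible choices do inflate the change contrast: up to 7.9% (knot at 6 months), 10.6% (knot at 12 months) and 9.7% (quadratic). The specification matters, and the sentence does not select a safe one.

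A reader might also infer from the count of seven points that the 5- and 10-year visits will distort the primary result. They cannot do so in any material way. Last patient out is March 2021 and database lock April 2021, so no 10-year data and almost no 5-year data can exist by then. The late results are a separate paper ("A randomized controlled trial – results at 5 years", section 14.2).

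Finally, the inflation needs the change reading. On the section 6.2 reading, step or plateau with a months slope is conservative (3.1-4.0%). This stands, and it limits the claim.

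**Conclusion.** The point holds as a cheap improvement. The stated rule can misstate the SE of the primary contrast, in a direction that depends on the contrast, the time scale and how patients truly differ. For change, the assumed step or plateau responses give 6.6-10.5% with a months slope, 3.9-5.2% with log time and 7.5-13.4% with the slope dropped. For the 24-month difference with a months slope, the SE is about 5-10% too wide. Compound symmetry shows no error, and decaying correlation with a months slope kept is slightly conservative.

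All sizes rest on assumed covariances scaled to an SD of change of 15. The documents do not support saying that the planned test is anti-conservative; they support only that its error rate is not secured. The sample size is unaffected.

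**What to change.** Replace the random-effects sentence in section 7.2 with wording such as:

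> *Visit is categorical. The within-patient covariance over the five visits to 24 months is unstructured (REML, Kenward-Roger degrees of freedom). No covariance term is selected by significance. If the model does not converge, compound symmetry with small-sample-corrected robust standard errors is used. The 24-month result is taken from this five-visit model.*

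With complete data the change contrast then equals a two-sample t-test on change, which is what the synopsis says it should resemble.

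**Cost.** Wording only; SAS 9.4 is already named and N does not change. There are 5 × 6 / 2 = 15 covariance parameters instead of at most 4 with a single slope, feasible with 82 patients.

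**Limits of the testing.** The simulations used completers minus 2 degrees of freedom, not Kenward-Roger, and loss completely at random only. The fallback, with a Kauermann-Carroll correction, gave 4.6-5.7% for both contrasts in all eight patterns. Its point estimates lean on compound symmetry if loss depends on outcome, so it should remain a fallback.

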	cm2, defect ICRS grade 3-4, ligamentous stable knee, range of motion 5-105°, Lysholm score < 75 and informed consent. Exclusion: Osteoarthritis, rheumatoid or other systemic arthritis, malalignment > 5° measured on x-rays, BMI > 30, comorbidities that may influence surgery or rehabilitation, pregnancy, inability to complete questionnaires or rehabilitation, serious alcohol or drug abuse, previous cartilage surgery to the chondral defect except OCD surgery.
Treatment Groups:	2 treatment groups with 41 patients in each group.
Visit Schedule:	3 months (\pm 2 weeks), 6 months (\pm 4 weeks), 12 months (\pm 6 weeks) and 24 months (\pm 8 weeks). All will be invited to participate in late controls after 5 and 10 years.
Safety Assessments:	If any unforeseen complication outside normal clinical practice occurs, the sponsor representative will be contacted as soon as possible with a parallel message to the local coordinators at the involved hospitals. During each follow up, there will be a case report form (CRF) regarding complications and safety.
Sample Collection:	A 5 mL venous blood sample will be drawn on the day of operation. The blood sample will be centrifuged before serum is pipetted in a sterile tube. The serum will be analyzed at Oslo University Hospital – Rikshospitalet on the cartilage biomarker microRNA-140 (miR-140). During the open chondrocyte implantation the excess cartilage debrided from the rim of the lesion will be sent for similar microRNA-140 (miR-140) analysis. (applicable for the 41 patients in the ACI arm only)
Overview of Statistical Plan:	If normal distribution, aims will be analyzed using linear mixed models (LMM), and the primary aim will be performed as a post hoc test for the LMM, similar to performing a two-sample t-test. If no normal distribution, analysis will be performed using Mann-Whitney U-test.
Sample Size Determination:	Detecting a difference of 10 in primary aim with 80% power using a standard deviation of 15. A $p < 0,05$ is statistically significant.

Interim Analysis:	This gives 37 patients in each group, adding 10% drop out meaning 41 patients in each group and 82 in total.
Ongoing Data Monitoring Plan:	No interim analysis will be done.
Study Stopping Rules:	Monitor at Akershus University Hospital.
End of Study:	Inclusion of 82 patients.
Operational Risk Analysis:	The end of this study is 24 months after the last included patient.

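### The primary comparison is KOOS QoL at 2 years in sections 6.2 and 7.1, but the sample size in 7.3 is for change from baseline, and the 7.2 model allows either

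*Protocol*

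**What the plan says.** **Score at 2 years.** Section 6.2 states that "the primary aim is the difference in KOOS QoL subscore in the ACI group compared to the AD group at 2 years follow up". The null hypothesis in 7.1 concerns the same subscore for a defect "in the weight bearing area of the knee 2 years after surgery". Neither section mentions change.

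**Change from baseline.** Section 7.3 assumes a between-arm difference of 10 points in change and an SD of change of 15. With 80% power and 5% significance it reaches 37 per group, and 82 in total after adding 10% for loss. The synopsis null hypothesis is looser: "There is no difference in KOOS QoL after ACI or AD from baseline to 24 months after surgery".

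**The model.** Section 7.2 describes a mixed model "with 5 (7) measurement points, repeated observations will be available for each patient". The five are baseline and 3, 6, 12 and 24 months; 5 and 10 years make seven. On the mean structure it says: "Fixed effects for time (likely non-linear) and group will be included together with the interaction between the two". The interaction serves as an omnibus test. On contrasts it says: "Relevant pairwise comparisons will be performed by deriving individual time point contrasts within each study arm". On covariates: "The estimates will further be adjusted for possible confounders such as age of the patient and severity of the cartilage lesion". The synopsis adds that "the primary aim will be performed as a post hoc test for the LMM, similar to performing a two-sample t-test", without saying whether the tested quantity is score or change.

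**The concern.** The score at 24 months and the change to 24 months are different test statistics. Under randomisation they estimate the same treatment effect, but they differ in precision and in how they respond to a chance baseline difference between arms. They can fall on opposite sides of p = 0.05 in the same data set.

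Two things are at stake. First, the 80% power was computed for one quantity while the declared primary comparison is the other. Second, one fitted model supplies both contrasts, and 7.2 does not name the between-arm contrast that carries the primary test. If the choice were left until the data were seen, the 5% error rate would not be held.

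**Working it through.** **Inputs from the protocol (7.2, 7.3):** difference d = 10, SD of change 15, two-sided 5%, 37 analysed per arm.

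**Assumed, not in the protocol:** r, the correlation between baseline and 24-month KOOS QoL, 0.3 to 0.7; k, the baseline SD divided by the 24-month SD, 0.7 to 1.2. Complete data.

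**Step 1: reproduce the stated size.** The normal approximation gives 2 × (15 × (1.960 + 0.842)/10)² = 35.3, so 36 per arm. The exact noncentral t gives power 79.7% at 36 and 80.8% at 37. Adding 10%: 37 × 1.1 = 40.7, so 41 per arm and 82 in total. The plan's figures hold for the change contrast.

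**Step 2: translate to the other contrasts.** With 24-month SD s, the variance of change is s²(1 + k² − 2kr). Fixing the SD of change at 15:

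- 24-month SD: s = 15/√(1 + k² − 2kr)
- residual SD after adjusting for baseline: s√(1 − r²)

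Example, r = 0.7 and k = 1: s = 15/√0.6 = 19.4; residual SD = 19.4 × √0.51 = 13.8.

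**Step 3: power at 37 per arm** (noncentral t; 72 df for the score, 71 for the adjusted difference). The change contrast has 80.8% in every row.

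| k | r | 24-month SD | Residual SD | Power, unadjusted score | Power, baseline-adjusted |
|---|---|---|---|---|---|
| 0.7 | 0.3 | 14.5 | 13.8 | 83.3% | 86.6% |
| 0.7 | 0.5 | 16.9 | 14.6 | 71.0% | 82.7% |
| 0.7 | 0.7 | 21.0 | 15.0 | 52.4% | 80.7% |
| 1.0 | 0.3 | 12.7 | 12.1 | 91.7% | 93.9% |
| 1.0 | 0.5 | 15.0 | 13.0 | 80.8% | 90.4% |
| 1.0 | 0.7 | 19.4 | 13.8 | 59.2% | 86.6% |
| 1.2 | 0.3 | 11.4 | 10.9 | 96.0% | 97.3% |
| 1.2 | 0.5 | 13.5 | 11.7 | 88.3% | 95.3% |
| 1.2 | 0.7 | 17.2 | 12.3 | 69.4% | 93.2% |

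The unadjusted score exceeds 80% in five of the nine settings. It matches or beats change exactly when s ≤ 15, that is, when k ≥ 2r.

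**Step 4: how often the two tests disagree.** In simulated trials over the same nine settings, t-tests on score and on change gave different verdicts at p < 0.05 in about 15 to 36% of trials with a true difference of 10. With no true difference, at least one of the two was significant in about 8 to 10%.

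**Step 5: what the 7.2 model delivers.** With time as categories and complete data, a model with time, group and their interaction reproduces the arm means at each visit. Its 24-month contrast is then the raw score difference, and its change contrast is the raw difference in change. Neither is adjusted for baseline.

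**Step 6: why adjustment removes the choice.** Write y for the 24-month score, b for baseline and g for arm. If y = a + τg + βb, then y − b = a + τg + (β − 1)b. The coefficient τ, its estimate and its standard error are the same, so score and change become one analysis.

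**The case against.** **The protocol does name a primary comparison.** A reader might infer that no passage says which contrast is primary. Section 6.2 does, 7.1 agrees with it, and the synopsis likens the test to a two-sample comparison. What remains is narrower: the sample size is for another quantity, the synopsis hypothesis is loose, and 7.2 does not tie its model to the comparison in 6.2. The synopsis wording could even refer to the follow-up period, so the conflict rests on 6.2 and 7.1 against 7.3.

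**Baseline adjustment is SAP material.** This stands. Its absence from 7.2 is not a fault by itself, and the covariate list there is open and does not exclude baseline KOOS QoL. Adjustment is raised here because it resolves the conflict. An SAP alone could not: whichever contrast it chose, it would disagree with one of the protocol sections.

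**The practical effect is limited.** This stands in part. The expected difference is the same for both contrasts and no interim analysis is planned. A reader might infer that the trial is underpowered, or that the test will be picked after the results are seen. The documents support neither: the score's power falls on both sides of 80% depending on r and k, and nothing indicates later selection. The 8 to 10% rate describes what would happen if the choice were left open.

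**The ranges are assumptions.** True. The larger gains of adjustment over change need k of 1 or more, while the Lysholm entry limit may, if anything, narrow the baseline spread. At k = 0.7 adjustment saves 15, 5 and 0% of the variance of change for r = 0.3, 0.5 and 0.7. The case for it therefore rests mainly on removing the ambiguity.

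**Conclusion.** The inconsistency is real and lies within the current protocol text. The primary comparison is a score at 2 years in 6.2 and 7.1, and the sample size in 7.3 is for change. The 7.2 model supplies both and does not name the between-arm contrast to be tested.

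There is no bias, and 37 per arm is right for change. The stated 80% is not secured for the unadjusted 24-month score: its power is 52 to 96% over the assumed r and k. A baseline-adjusted difference has 81 to 97% over the same range. Its lowest value, 80.7% at r = k = 0.7, is in effect the power of change. These ranges illustrate the dependence on r and k and are not estimates for this trial. This should be corrected, but it does not threaten the design.

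**What to change.** **Minimum:** state the same primary quantity in the synopsis, 6.2, 7.1 and 7.3. This alone cures the contradiction.

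**Preferred wording for that quantity:** *the ACI minus AD difference in KOOS QoL at 24 months, adjusted for baseline KOOS QoL.*

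**In 7.2:** name this between-arm 24-month contrast as the primary test, and fit it in one of two ways:

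1. keep baseline as a response visit and give both arms a common baseline mean; or
2. enter baseline KOOS QoL and its interaction with visit as covariates, and remove baseline from the response visits.

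Baseline should not be both a response and a covariate.

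**In 7.3:** say that the 80% refers to the unadjusted change contrast and that the adjusted contrast has at least about that power.

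**Cost:** wording in four places and one model sentence. Baseline KOOS QoL is already collected before surgery (6.3), hence before the in-theatre randomisation (5.2). No further data or patients are needed, N = 82 is unchanged, and the adjustment uses about one degree of freedom.
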